### **7.7.2. Analysis of TCN resistance in CT cases**

The analysis of TCN resistance in CT cases will include all positive CT cases after baseline. TCN resistant CT will be defined by the detection of *tetC* gene cassette.

Descriptive statistics: Tabulations of TCN resistance in CT cases (TNC resistance testing = missing, not resistant, resistant) will be reported at baseline, 3, 6, 9 and 12 month visits in each arm.

Statistical analysis: Assessment of difference in odds of TCN resistance by arm across all post baseline visits with infection will be assessed by estimating the odds of TCN resistance using logistic regression, with repeated measures methods (GEE) if repeat infections occur.

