**Table 1. Evidence base for antibiotic prophylaxis for STI prevention**

Study	Population	Intervention	Results
Molina et al.	MSM taking PrEP, France (n=232)	Single-dose 200 mg doxycycline after condomless sex vs. no medication (open label)	47% reduction in curable STIs, with greatest reductions for chlamydia (70%) and syphilis (73%). Medication was well-tolerated & highly acceptable. Limited assessment of resistance in STIs.
Bolan et al.	HIV+ MSM with history of syphilis, US (n=30)	100 mg doxycycline daily vs. no medication (open label)	73% reduction in STIs. No self-reported behavior change.
Steen et al.	Female sex workers, multinational (meta-analysis of 14 studies)	Single dose or monthly antibiotic treatment (most used azithromycin with ciprofloxacin or cefixime)	40-60% reduction in Neisseria gonorrhoeae & 47-62% reduction in Chlamydia trachomatis . No evidence of risk compensation. Few studies assessed STI antibiotic resistance.

**The potential emergence of antimicrobial resistance selected by intermittent antibiotic use is an important concern for STI PEP.** Following the initial study of empiric single-dose antibiotics to reduce gonorrhea among sex workers in the Philippines, follow-on studies showed some women (12%) reported self-prescribing antibiotics for empiric treatment, and high rates of penicillin-resistant *N. gonorrhoeae* were associated with self-prescription. Today, multi-drug resistant *N. gonorrhoeae* is a growing international public health issue. Notably, the IPERGAY results found no reduction in gonorrhea, which was expected given the high percentage (56%) of *N. gonorrhoeae* in Europe are already resistant to tetracyclines. In Africa, antimicrobial resistance data are more sparse, but high prevalence (73-97%) detection of plasmid mediated tetracycline-resistant *N. gonorrhoeae* has been seen, including in our preliminary results from Kenya. Importantly, and in contrast, *C. trachomatis* has never been reported to express resistance to doxycycline worldwide, although *Chlamydia suis* with tetracycline resistance has been documented in pigs. Rigorous studies are needed to quantify resistance in populations exposed to dPEP and whether dPEP use results in additional resistance.

**Doxycycline PEP could be especially impactful for African women using PrEP.** Essentially all global

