**State-of-the-art assessment of antimicrobial resistance.** Over the past 14 years, [name] has worked extensively in the field of gonococcal antimicrobial resistance (AMR). [name] laboratory characterizes molecular mechanisms of AMR in *N. gonorrhoeae* isolates and is a core laboratory for CDC's national gonococcal AMR surveillance project, and he has identified isolates with unique AMR profiles. Preliminary results from frozen STI+ endocervical swab samples from Kenyan women in our Partners PrEP Study (i.e., \*not\* using dPEP) were tested for tetracycline resistance using the molecular methods: 50 with *N. gonorrhoeae* and 10 with *C. trachomatis*. Detection of tetracycline-resistance was high for *N. gonorrhoeae* (*tet*(M)=48/50, 96%), suggesting resistance may be at a ceiling in the community already, prior to dPEP use, but also that dPEP may not be effective against *N. gonorrhoeae*. No *C. trachomatis* organisms had resistance (*tet*(C)=0/10, 0%).

**Mathematical modeling and costing studies help to define optimal models for PrEP delivery.** Led by [name], we have used costing methods and mathematical modeling to address key questions related to how to best deliver PrEP. For serodiscordant couples, we found the cost of PrEP per infection averted is significantly offset by future savings in ART costs, especially time-limited PrEP – used prior to and early after ART initiation by an HIV infected partner, when risk is highest. These results were a key basis for designing our “PrEP as a bridge to ART” strategy in the Partners Demonstration Project. Second, we used methods for development of clinical prediction rules to derive a risk scoring tool for couples. Our work has been a model for risk scores for other populations – for example, the VOICE score for women at risk – and for programmatic prioritization of subpopulations for PrEP. Third, micro-costing, time and motion work, and mathematical modeling have helped define the annual cost of PrEP (~US\$100) for the Kenya Ministry of Health.

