#### *Potential for drug resistance*

The potential for inducing drug-resistant STIs is an important concern for dPEP. On one hand, antibiotic resistance to tetracycline-class drugs is selected relatively easily in some bacteria (e.g., *N. gonorrhoeae*); on the other hand, resistance for *N. gonorrhoeae* is common globally, making additional resistance selection unlikely, but other organisms (e.g., *C. trachomatis*) have never demonstrated resistance. Syphilis (*Treponema pallidum*) is at risk of developing tetracycline resistance; however, we anticipate very low rates (<2%) of syphilis and thus in this population the risk of developing resistance is very low. Moreover, if dPEP is successful in preventing STIs, resistance may not occur, as selection should only happen if infection is established and replication occurs despite antibiotic pressure. Overall, we feel there are both important knowns and unknowns that define equipoise for this question, and we have put strong strategies in place to manage and mitigate potential resistance risks.

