### Statistical power and analysis

We propose a standard randomized superiority design, comparing dPEP to standard of care. The primary trial outcome will be the combined incidence of incident *C. trachomatis*, *N. gonorrhoeae*, and syphilis, compared between the randomization arms, to mirror the IPERGAY approach; analyses will also test each pathogen alone. We have been conservative in planning: first, we have planned for an STI incidence of 22% per year in the standard of care arm, which is less than the *C. trachomatis* incidence seen in our recent studies (**Table 3**) and second, we will calculate based on time to first incident STI alone, although we anticipate that some women will have repeat STIs contributing additional events and additional statistical power. We have planned for a 50% effect, comparable to the IPERGAY results and sufficiently great for public health benefit, but we anticipate that the *C. trachomatis* effect could be >50%, given universal susceptibility to doxycycline and

IPERGAY findings. With 80% power, 10% loss-to-follow-up, incidence of 22% vs. 11% (n=44 vs. 22 cases), and a two-sided alpha of 0.05, a sample size of n=550 is needed (n=275 per arm).

*Primary Analysis:*

We will analyze the composite endpoint of any of the three STIs as well as for *C. trachomatis* alone, and we will continue until there are sufficient *C. trachomatis* events (n=66) given the high incidence of this pathogen and its importance for reproductive morbidity (the consequence of which will be that the total number of events in the composite of *C. trachomatis*, *N. gonorrhoeae*, and syphilis will be greater than n=66). Analyses will be intention-to-treat, including women whether or not they continue dPEP (as well as whether or not they continue PrEP). STI incidence will be compared between arms using repeated measures analysis of proportions (e.g., generalized estimating equations [GEE]), given possibility of repeat infection within individuals. Per-protocol and adjusted analyses will be done as needed, controlling for potential confounders: demographics (e.g., age, education), sexual behavior (e.g., condom use, # partnerships), and beliefs (e.g., risk perception, dPEP/PrEP efficacy). SAS or R will be used.

*Secondary Analyses:*

Safety: Safety outcomes (i.e., AEs, tolerability, pregnancy, behavior) will be compared between arms using repeated measures analyses.

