## **4. PLANNED ANALYSES**

### **4.1. Interim Analyses**

The trial will be monitored by an independent data monitoring committee approximately every 6 months. The trial plans to continue until we have established definitive efficacy results, whether effective or ineffective, for both CT alone and for any STI. Two formal interim monitoring times are planned, when 1/3 and 2/3 of the follow-up visits have been completed, with stopping rules based on consideration of both the primary outcome and the CT outcome alone. Because the outcomes are highly correlated, no adjustment for multiple comparisons is planned. O'Brien-Fleming boundaries will be used, with stopping based on the alpha spending corresponding to observed p-values in the efficacy analyses. Stopping for both efficacy and lack of efficacy will be considered; however, a decision to stop for efficacy will need to balance the need for evidence assessing the potential harm of acquired tetracycline resistance.

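### SAP 7.7.2 compares CT resistance only by logistic regression or GEE, which gives no usable result if one or both arms have zero tetC-positive cases, a foreseeable outcome

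*SAP*

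**What the plan says.** SAP 7.7.2 covers all CT-positive cases after baseline. "TCN resistant CT will be defined by the detection of" the tetC gene cassette. Counts of missing, non-resistant and resistant results "will be reported at baseline, 3, 6, 9 and 12 month visits in each arm". The difference in odds between arms "will be assessed by estimating the odds of TCN resistance using logistic regression, with repeated measures methods (GEE) if repeat infections occur".

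The SAP gives no interval for a proportion, no exact or penalised method and no rule for empty cells. The protocol (resistance testing under the laboratory procedures, and section 10.0) plans to compare rates of resistant events between arms and is equally silent on zero counts.

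The protocol's evidence on CT resistance all points one way:
- Section 1.0 Background: *C. trachomatis* "has never been reported to express resistance to doxycycline worldwide".
- Section 1.0, preliminary results: tet(C) in 0 of 10 CT-positive samples from Kenyan women not using dPEP.
- Rationale, potential for drug resistance: organisms such as *C. trachomatis* "have never demonstrated resistance".
- Laboratory procedures: the only determinant reported in the genus was found in a pig species.
- Section 10.0: the CT effect could exceed 50%, "given universal susceptibility to doxycycline".

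Resistance is among the primary objectives in protocol section 3.0 and secondary in SAP 2.1.2. SAP 4.1 adds that "a decision to stop for efficacy will need to balance the need for evidence assessing the potential harm of acquired tetracycline resistance".

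**The concern.** A logistic model needs resistant and non-resistant cases in both arms to give a finite odds ratio for arm. If neither arm has a tetC-positive case, the outcome does not vary. If only the dPEP arm has one, which is the pattern of most interest, the odds ratio is infinite. The one inferential method in 7.7.2 therefore breaks down in the situations that the background evidence makes most plausible.

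At stake is what the trial can say about CT resistance. A zero count supports a statement about how much resistance has been ruled out, and that depends on how many infected women were tested. If dPEP prevents CT, the dPEP arm has few cases and its limit is wide. A zero without a limit can be taken for more reassurance than the data carry, and SAP 4.1 and the DSMB section of the protocol both give resistance evidence a part in early stopping.

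**Working it through.** **1. The plan's own event figure.** The inputs are in SAP 3.3.1: 50% reduction, two-sided alpha 0.05, 80% power, 446 women (223 per arm), 10% loss, control incidence 22%.

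- Events (Schoenfeld, 1:1): 4 × (1.960 + 0.842)² / (ln 0.5)² = 65.4, so 66. This agrees with the SAP.
- Split: 223 × 0.9 = 200.7 evaluable per arm; × 0.22 = 44.2 and × 0.11 = 22.1, so 44 vs 22. This also agrees.

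The split is stated for any STI. SAP 3.3.1 also requires CT in at least 66 women, so applying 44 vs 22 to CT at a 50% effect is an assumption.

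**2. The specified model with sparse data.**

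| Resistant, dPEP vs SOC | Logistic / binomial GLM | GEE, robust SE | Fisher exact p |
|---|---|---|---|
| 0/22 vs 0/44 | Logistic did not converge (arm SE 1,130,481); GLM log OR about 0, SE 34,209 | log OR 0, SE 0.26 | 1.00 |
| 1/22 vs 0/44 | GLM log OR 20.5, SE 11,979 | log OR 21.5, SE 1.02 | 0.33 |
| 3/22 vs 0/44 | GLM log OR 21.7, SE 11,979 | log OR 22.7, SE 0.62 | 0.034 |

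The GEE column is the more misleading one. In the first row it gives an odds ratio of 1.0 with a nominal interval of exp(±1.96 × 0.26), about 0.6 to 1.7, from data with no events. That standard error equals √(1/22 + 1/44) = 0.261, so it reflects only the numbers tested. In the second row a single resistant case gives a nominal z of 21.5/1.02, about 21, where Fisher's exact test gives p = 0.33. These outputs come from one software package; others may stop with an error instead.

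**3. What zero resistant cases would exclude.** The exact (Clopper-Pearson) two-sided 95% upper limit for 0/n is 1 − 0.025^(1/n).

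| CT cases tested, none resistant | Basis | Upper limit |
|---|---|---|
| 15 | dPEP arm, 70% CT effect (assumed split of 66: about 15 vs 51) | 21.8% |
| 22 | dPEP arm, 50% effect, planned minimum | 15.4% |
| 33 | dPEP arm, half as many cases again | 10.6% |
| 44 | dPEP arm, twice the minimum | 8.0% |
| 66 | both arms pooled | 5.4% |

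For 0/22 vs 0/44, a Newcombe (score, not exact) 95% interval for the difference dPEP minus SOC runs from −8.0 to +14.9 percentage points.

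If the true proportion resistant in the dPEP arm were 5%, zero of 22 would be seen with probability 0.95²² = 0.32; at 10% it would be 0.90²² = 0.10.

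**4. Range from the protocol's CT incidence.** Table 3 gives 27% to 53% per year. By simple scaling at 50% effect and 10% loss, dPEP-arm cases are 200.7 × 0.27 × 0.5 = 27 to 200.7 × 0.53 × 0.5 = 53 (limits 12.8% to 6.7%). With the protocol's 275 per arm they are 247.5 × 0.27 × 0.5 = 33 to 247.5 × 0.53 × 0.5 = 66 (limits 10.6% to 5.4%).

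**The case against.** A reader might infer that the protocol expects no tetC-positive case in either arm. The documents do not support that. Their evidence describes CT not exposed to dPEP, and the ten preliminary samples alone exclude only a prevalence above 1 − 0.025^(1/10) = 30.8%. Whether dPEP selects resistance is itself an objective, and the rationale says important unknowns remain. Zero is foreseeable, not forecast.

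Nor is the plan left without information. The 7.7.2 tabulation gives resistant and tested counts by visit and arm, from which a reader could compute a limit. That stands, but no overall denominator is fixed for repeat infections, test-of-cure swabs (included in SAP 2.2.5) or missing results, and no interval is planned. The SAP may also be revised until database lock, so there is room for the correction.

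Three further points have weight. The 22 cases are a conservative any-STI number, and step 4 suggests more CT cases are likely, although a larger CT effect or missing results would cut them. The SAP ranks resistance as secondary, and SAP 4.1 refers to tetracycline resistance in general, not to this CT model. Finally, the limit depends on the denominator. If the protocol's rate of resistant events were taken per woman (it does not say), 0 among about 201 evaluable dPEP women would have an upper limit of 1.8%. The figures here concern the proportion among CT-infected women, the quantity that 7.7.2 analyses.

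**Conclusion.** The concern holds. The only between-arm analysis named in 7.7.2 gives no finite maximum-likelihood estimate when one or both arms have no resistant case, and its GEE form can print an odds ratio and interval without meaning. This is a stated method that fails in a foreseeable situation, not merely missing detail.

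With 22 to 44 CT cases tested in the dPEP arm and none resistant, resistance of up to 15.4% to 8.0% among them is not excluded. The range rests on applying the any-STI figure of 22 to CT as the lower end, on independent observations and on complete resistance results. More cases narrow it; a larger CT effect or missing results widen it (21.8% at 15 cases).

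It would go too far to say that the trial will yield nothing on CT resistance, or that 15.4% is the limit it will reach. The counts will exist, and 66 women with CT is a minimum. The primary efficacy analysis is not affected.

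**What to change.** In SAP 7.7.2:
- Make the main analysis the number resistant over the number tested after baseline in each arm, with one isolate per woman (for example the first post-baseline CT infection, or any resistant versus none) so that observations are independent.
- Give an exact (Clopper-Pearson) 95% confidence interval per arm and an exact interval for the difference.
- Tabulate all infections, including repeats, as a supplement, and say how missing results and test-of-cure swabs are handled.
- Fit a penalised (Firth) or exact comparison only if resistant cases occur.
- State that the denominator is CT-infected women, a post-randomisation subset, and that with zero cases the conclusion is the upper limit in the dPEP arm.

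The cost is SAP wording only, with no new visits, samples or assays. The downsides are that an upper limit reads less favourably than a plain zero per cent, and that repeat infections drop out of the main interval.

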## **8. SAFETY AND TOLERABILITY**

Statistical tests are not planned for adverse event comparisons between arms. Safety and tolerability will be assessed in the ITT cohort, given the open label nature of the cohorts.

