#### **Clinical study care**

**Review of current medications:** All participants will have current medications reviewed at screening for possible drug interaction with doxycycline. At subsequent quarterly visits, participants randomized to dPEP will have current medications reviewed and any new medications will be assessed for possible drug interactions.

**STI symptom screen:** Participants will be asked about current STI symptoms including vaginal discomfort, dysuria, rash, vaginal discharge, rectal pain, pelvic pain, and genital lesions.

**General symptom assessment:** At each visit, participants in both study arms will be asked about possible doxycycline side effects, including esophagitis, rash, gastrointestinal symptoms, photosensitivity, headache, and vaginal yeast infection. Control arm participants will be asked about these symptoms to establish a comparator for non-specific symptoms which can occur in the absence of doxycycline.

**Risk reduction counseling:** At each visit, staff will counsel participants about risk reduction and HIV and STI prevention and will receive condoms.

**Pill count and dPEP adherence assessment:** Participants assigned to dPEP will be asked to bring their doxycycline blister packs in at each visit for a pill count. While completing the timeline follow-back calendar to record sexual exposures will be asked when dPEP was taken and if each sex act were covered by dPEP in the past 3 months.

**PrEP adherence assessment and counseling:** All participants will receive quarterly PrEP adherence assessment (Likert scale) and adherence counseling.

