### Secondary outcomes:

- Safety: Safety assessment will be measured in both arms: serious adverse events (SAEs), related all AEs and discontinuations (in the dPEP arm only), and a standardized symptom assessment for doxycycline-specific side effects (e.g., nausea, pill esophagitis, photosensitivity, vaginal candidiasis).
- Acceptability: Longitudinal change in qualitative themes and associated barriers and facilitators
- Adherence: We will explore the self-reported measures and SMS data, defining adherence as the percentage of times that dPEP was taken following an episode of condomless intercourse. Stored vaginal swabs for Y chromosome testing can be available for later validation.
- Resistance: The detection of the plasmid-encoded *tet(M)* gene and/or *tetR* genetic resistance determinants is indicative of phenotypic resistance to tetracycline
- Cost: The incremental cost effectiveness ratio (ICER) per incident STI case averted and DALY averted

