## 2. STUDY OBJECTIVES AND ENDPOINTS

### 2.1. Study Objectives

#### 2.1.1. Primary Efficacy and Safety Objectives

1. Evaluate the effectiveness of doxycycline post-exposure prophylaxis (PEP) to reduce STI infections in HIV-uninfected Kenyan women taking HIV PrEP
2. Assess the safety, tolerability, and acceptability of dPEP

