#### **8.1.2. Adverse Event Summary Tables**

The number of SAEs will be tabulated by grade and arm. For the dPEP arm, related AEs will be tabulated by grade (see below of definition of relatedness).

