## **8.3. Tolerability**

Tolerability is assessed for participants on the dPEP arm through

- a self-reported response to whether a participant did not take dPEP because of side-effects.

Descriptive: The Yes/No responses of dPEP side effects will be tabulated for each study visit among dPEP participants

- Symptoms from the side-effect questionnaire

Descriptive: Symptoms, collected at each visit, will be tabulated for each arm

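### SAP 8.3 tabulates solicited doxycycline symptoms by arm but gives no between-arm estimate, interval or repeated-measures model, although the protocol promises such a comparison

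*SAP*

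**What the plan says.** **Protocol.**
- Section 10.0, safety paragraph of the secondary analyses: "Safety outcomes (i.e., AEs, tolerability, pregnancy, behavior) will be compared between arms using repeated measures analyses".
- Clinical study care, general symptom assessment: both arms are asked about possible doxycycline side effects at each visit, and the reason for asking the control arm is given: "Control arm participants will be asked about these symptoms to establish a comparator for non-specific symptoms which can occur in the absence of doxycycline".
- Section 10.0, secondary outcomes: related adverse events and discontinuations are assessed in the dPEP arm only.

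**SAP.**
- Section 2.1.1 lists among the primary objectives "Assess the safety, tolerability, and acceptability of dPEP".
- Section 2.2.3 names the tolerability endpoints: discontinuation (dPEP arm only), treatment for Candida, and solicited side effects.
- Section 8: "Statistical tests are not planned for adverse event comparisons between arms". Safety and tolerability are assessed in the ITT cohort.
- Section 8.1.2: "The number of SAEs will be tabulated by grade and arm".
- Section 8.3: "Symptoms, collected at each visit, will be tabulated for each arm".
- Sections 9.1 and 9.1.1 compare sexual frequency and condom use by arm with GEE.
- The revision log in Section 10 does not mention a change to the safety comparison.

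**The concern.** A control-arm symptom assessment is worth its cost only if the arms are contrasted. Nausea, headache and yeast infection occur without doxycycline, so the quantity of interest is the excess in the dPEP arm and how precisely it is known. The protocol recognises this and commits to a repeated-measures comparison. The SAP replaces that with tables and gives no reason.

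Each woman can report a symptom at up to four follow-up visits. Section 8.3 does not say whether the tables are by visit or pooled. If they are pooled, or if a reader adds up the visits, the printed counts do not show how far reports from the same woman go together, so a correct pooled interval cannot be derived from them.

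At stake is the precision attached to the tolerability result, under an objective that the SAP ranks as primary. Two further outcomes fall through the same gap: Candida treatment and pregnancy.

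**Working it through.** **1. What became of each outcome in the protocol's safety sentence**

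| Outcome in the protocol | Treatment in the SAP |
|---|---|
| Adverse events: SAEs | Counts by grade and arm, no tests (8, 8.1.2) |
| Adverse events: related | dPEP arm only, as in the protocol, so no contrast is possible |
| Tolerability: solicited symptoms | Tabulated for each arm, no estimate or model (8.3) |
| Tolerability: Candida treatment | Listed in 2.2.3, no analysis in 8.3 |
| Pregnancy | A censoring rule (7.5.2) and a reason for stopping drug (8.1.3); no comparison by arm |
| Behaviour | GEE by arm (9.1, 9.1.1) |

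Behaviour is the only one that keeps a between-arm model.

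**2. Would a symptom contrast be informative?**

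The plan states no figure for safety precision, so there is none to reproduce.

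Inputs from the SAP: 223 women per arm and 10% loss (3.3.1); follow-up visits at months 3, 6, 9 and 12. Assumptions: a symptom reported at 5% of control visits and 10% of dPEP visits, and a design effect D for repeated reports. Neither document gives symptom rates or a within-woman correlation.

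- Women per arm: 223 × 0.9 = 200.7, about 201.
- Visits per arm: 201 × 4 = 804, taking all four visits as attended.
- Variance term: 0.05 × 0.95 + 0.10 × 0.90 = 0.1375.
- SE of the difference: √(0.1375 / 804 × D) = 0.0131 × √D.
- 95% half-width: 1.96 × SE.

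With four visits and a common within-woman correlation ρ, D = 1 + 3ρ.

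| D | ρ | Half-width (points) | Interval around a 5-point excess |
|---|---|---|---|
| 1 | 0 | 2.6 | 2.4 to 7.6 |
| 1.5 | 0.17 | 3.1 | 1.9 to 8.1 |
| 2 | 0.33 | 3.6 | 1.4 to 8.6 |
| 4 | 1 | 5.1 | −0.1 to 10.1 |

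A reader who pooled the visits and ignored repeats would quote the first row. The correct interval is wider by √D: 1.2 times at D = 1.5 and 2 times at D = 4.

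**3. Check at participant level**

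Counting each woman once (symptom ever or never), with 223 per arm and equal risk p in both arms, the half-width is 1.96 × √(2p(1 − p)/223). For assumed p of 5%, 10% and 20% this gives 4.0, 5.6 and 7.4 points. With 200 per arm it gives 4.3, 5.9 and 7.8. An estimate for common symptoms is informative on either basis.

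**The case against.** There is a fair case for the SAP as it stands, and several stronger readings fail.

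- **A reader might infer that the SAP plans no between-arm safety comparison at all.** It does plan some. Behaviour, a safety outcome in the protocol, is modelled by arm, and SAEs and symptoms are shown by arm, which is a descriptive comparison.
- **A reader might take the sentence in Section 8 as barring a symptom contrast.** It excludes tests, and only for adverse events. It does not exclude estimates or intervals, and on inference for symptoms the SAP is silent. The gap is in 8.3.
- **A reader might conclude that the trial could not say how much of the symptom burden comes with dPEP.** By-arm proportions in a randomised trial show the raw difference. At any single visit each woman contributes one report, so an ordinary two-proportion interval is valid there. Only the summary over visits needs allowance for clustering. What is missing is a planned estimate and its precision.
- **SAEs are a different matter.** They are recorded as events, not asked for at each visit, and may be few. Counting them by arm without tests is defensible, and a GEE could be unstable.
- **Rank.** Safety is a primary objective in both documents, but the protocol's statistical section places it under secondary outcomes and secondary analyses.
- **Open-label self-report.** Women know their arm, so a confidence interval does not separate drug effect from reporting effect. This stands, but the raw tables share the bias.

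These points narrow the concern to solicited symptoms, Candida treatment and pregnancy. They do not explain why the protocol's commitment was dropped for those outcomes.

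**Conclusion.** The concern holds in limited form. For solicited symptoms the SAP offers tabulation where the protocol promises a repeated-measures comparison and collects control data for that purpose. Candida treatment lacks any stated analysis, and pregnancy lacks the promised comparison. The change is neither explained nor logged.

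The consequence is lost precision in reporting. It does not invalidate the tolerability result or touch the efficacy analysis. On the assumed rates of 5% and 10%, the planned data would place a 5-point excess within about 3 points at a modest design effect and about 5 points at the extreme. These sizes are illustrative, because symptom rates, correlation and visit completeness are all assumed. The textual mismatch depends on none of them. This is a minor point worth correcting before the analysis.

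**What to change.** In SAP 8.3:
- For each solicited symptom, report the between-arm risk ratio or risk difference with 95% CI over the month 3, 6, 9 and 12 visits, in the ITT cohort, using the GEE with robust standard errors of 7.5.1. An identity link gives the risk difference.
- Label these results descriptive and unadjusted for multiplicity, with no significance threshold, and note that open-label self-report may bias them.
- Keep the by-arm tables and state that they are by visit.
- Give Candida treatment and pregnancy a simple between-arm estimate with CI.

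SAEs may stay as counts by arm without tests; a participant-level risk difference with an exact CI can be added if wanted. Related adverse events stay in the dPEP arm only. If the team prefers tables alone, the SAP should say that it departs from the protocol's safety analysis and why, and record this in the revision log.

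The cost is a few extra model fits on data already collected, and several unadjusted intervals that readers must not treat as tests.
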